4.1 Substudies (if applicable)

Not Applicable.

5 STUDY ENROLLMENT AND WITHDRAWAL

Only subjects who meet all of the inclusion and none of the exclusion criteria will be eligible for enrollment into this study. No exemptions will be granted.

A total of 60 subjects will be enrolled. The study population will be enrolled from in and around Americaninhas, a town located in the Municipality of Novo Oriente de Minas, 500 km northwest of Belo Horizonte, the capital of the Brazilian state of Minas Gerais.

Volunteers agreeing to participate will first provide written informed consent and take a true/false comprehension questionnaire. The questionnaire will be administered orally in the case of illiterate volunteers, and for both written and oral questionnaires study staff will use incorrect answers to identify aspects of the study that require clarification and focus on those areas of the informed consent form for further review with the volunteer. All questionnaire questions must be answered correctly, and the informed consent form signed, prior to study screening and enrollment. Volunteers unable to read will place an imprint of their finger in the place of a signature; in addition, an independent witness, who is not a member of the study team, will sign the consent form to attest that the informed consent form was read to the volunteer, the volunteer's questions were answered, and the volunteer answered all comprehension questions correctly. The original signed informed consent form for each volunteer will be maintained as part of that volunteer's study records. A copy of the informed consent form will be provided to every volunteer.

Screening can occur up to 90 days prior to enrollment; enrollment/randomization, and administration of first dose of study products will occur on the same day.

5.1 Subject Inclusion Criteria

1. Males or non-pregnant females between 18 and 45 years, inclusive.
2. Good general health as determined by means of the screening procedure.
3. Available for the duration of individual subject study participation (13 months).
4. Willingness to participate in the study as evidenced by signing the informed consent document.

5.2 Subject Exclusion Criteria

1. Pregnancy as determined by a positive urine hCG (if female).
2. Subject unwilling to use reliable contraception (as described in Section 2.3.1) from 30 days prior to the first immunization and up until one month following the third immunization (if female and not surgically sterile, abstinent or at least 2 years post-menopausal, or determined otherwise by medical evaluation to be sterile).
3. Currently lactating and breast-feeding (if female).
4. Inability to correctly answer all questions on the informed consent comprehension questionnaire.

-
5. Evidence of clinically significant neurologic, cardiac, pulmonary, hepatic, rheumatologic, autoimmune, diabetes, or renal disease by history, physical examination, and/or laboratory studies (a history of essential hypertension that is well controlled by medication will not be considered exclusionary.)
 6. Has a diagnosis of schizophrenia, bipolar disease or other major psychiatric condition that would make compliance with study visits/procedures difficult (e.g., subject with psychoses or history of suicide attempt or gesture in the 3 years before study entry, ongoing risk for suicide).
 7. Known or suspected immunodeficiency.
 8. Laboratory evidence of liver disease (alanine aminotransferase [ALT] greater than 1.25-times the upper reference limit).
 9. Laboratory evidence of renal disease (serum creatinine greater than 1.25-times the upper reference limit, or more than trace protein or blood on urine dipstick testing with the exception of greater than trace blood detected in females during menses).
 10. Laboratory evidence of hematologic disease (absolute leukocyte count $<3200/\text{mm}^3$; absolute leukocyte count $>10.8 \times 10^3/\text{mm}^3$; hemoglobin $<11.4 \text{ g/dl}$ [females] or $<12.1 \text{ g/dl}$ [males]; or, platelet count $<130,000/\text{mm}^3$).
 11. Serum glucose (random) greater than 1.2-times the upper reference limit.
 12. Other condition that in the opinion of the investigator would jeopardize the safety or rights of a volunteer participating in the trial or would render the subject unable to comply with the protocol.
 13. Participation in another investigational vaccine or drug trial within 30 days of starting this study.
 14. Previous receipt of the *Na*-GST-1/Alhydrogel[®] hookworm vaccine.
 15. Volunteer has had medical, occupational, or family problems as a result of alcohol or illicit drug use during the past 12 months.
 16. History of a severe allergic reaction or anaphylaxis.
 17. Severe asthma as defined by the need for daily use of inhalers or emergency clinic visit or hospitalization within the last 6 months.
 18. Positive test for hepatitis B surface antigen (HBsAg).
 19. Positive confirmatory test for HIV infection.
 20. Positive confirmatory test for hepatitis C virus (HCV) infection.
 21. Use of corticosteroids (excluding topical or nasal) or immunosuppressive drugs within 30 days of the volunteer's expected first vaccination in this study or planned use up to one month following the last vaccination.
 22. Receipt of a live vaccine within past 4 weeks or a killed vaccine within past 2 weeks prior to the volunteer's expected first vaccination in the study.
 23. History of a surgical splenectomy.
 24. Receipt of blood products within the past 6 months.
 25. Anti-*Na*-GST-1 IgE antibody level above $0.35 \text{ kU}_A/\text{L}$ by the ImmunoCAP method.
 26. Anti-*Na*-APR-1 IgE antibody level above ELISA reactivity threshold.

5.3 Treatment Assignment Procedures

5.3.1 Randomization Procedures

Eligible volunteers will be asked to come to the clinic on their scheduled day of enrollment into the study (Day 0). If required, transportation to the clinic will be provided free-of-charge. One or 2 additional eligible volunteers above the number to be enrolled into a given Group may be scheduled as Day 0 visit alternates, if possible. After undergoing a clinical interview and physical examination to ensure that they remain eligible for participation in the study, that they have had blood collected for safety clinical laboratory and baseline immunogenicity assessments, and that females have had a urine pregnancy test performed that is documented to be negative, volunteers will be randomized and enrolled in the order that they present for vaccination.

Within each group, randomization will be done through use of a randomization code, furnished to the study vaccine manager by the data management center. Access to the randomization list will be exclusively limited to the study vaccine manager and assistant. Between vaccination days, the randomization list will be stored in a locked cabinet. The study vaccine manager and assistant will be unblinded, but will not be involved in further evaluation of study subjects or assessment of adverse events. Volunteers will not be considered enrolled in the study until they have received their first dose of vaccine. In the event that a volunteer is randomized but not enrolled on the day of first vaccination, they will be replaced with an eligible alternate. Enrolled subjects that leave the study for any reason following first vaccination will not be replaced. Any alternates not vaccinated will be invited to participate as members of the next Group. Any Group 6 alternates not vaccinated, and therefore not enrolled in the study, will be offered vaccination with a non-study, licensed vaccine such as the tetanus toxoid or influenza vaccine.

5.3.2 Masking Procedures

Due to the staggered, dose-escalation design of the trial, it will not be possible to blind to *Na*-APR-1 (M74)/Alhydrogel[®] dose assignment or GLA-AF co-administration assignment. That is, those subjects enrolled into Group 1 will receive either 10µg *Na*-APR-1 (M74)/Alhydrogel[®] administered to one arm and sterile saline administered to the alternate arm, or 10µg *Na*-APR-1 (M74)/Alhydrogel[®] in one arm and 100µg *Na*-GST-1/Alhydrogel[®] administered to the alternate arm. Subjects enrolled into Group 2 will receive either 10µg *Na*-APR-1 (M74) /Alhydrogel[®] plus 5µg GLA-AF administered to one arm and sterile saline administered to the alternate arm, or 10µg *Na*-APR-1 (M74) /Alhydrogel[®] plus 5µg GLA-AF in one arm and 100µg *Na*-GST-1/Alhydrogel[®] administered to the alternate arm, and so on.

Investigators and subjects will be blinded to the within-Group random allocation to receive co-administered sterile saline or *Na*-GST-1/Alhydrogel[®] until all subjects have completed their Day 140 visit, the safety and secondary immunogenicity outcomes (i.e., anti-*Na*-GST-1 and anti-*Na*-APR-1 (M74) IgG antibody results by ELISA) have been monitored and entered into the database, and the database has been “soft-locked” for interim analysis. Procedures to maintain blinding include administering two injections to all subjects at each vaccination point. For this, sterile saline will be co-administered to those subjects randomized to receive *Na*-APR-1 (M74) without co-administration of *Na*-GST-1.

The study vaccine manager will also prepare all investigational product doses (vaccine or sterile saline placebo) in a separate room, and will hand filled syringes to the vaccinator(s). Since the 10 and 30µg doses of the *Na*-APR-1 (M74) formulations are of different volumes (0.1 and 0.3ml, respectively for administration without GLA-AF) than that of *Na*-GST-1, the contents of all syringes will be disguised using opaque tape. As a further precaution, the vaccinator(s) will not be involved in assessments of reactogenicity or adverse events.

Investigators will be unblinded after all subjects have had their study Day 140 visit. After this point, the study will be single-blinded (i.e., subjects will remain blinded to what products they received). The principal justification for unblinding the investigators before the final study visit has been completed is that the safety and immunogenicity data acquired during the vaccination phase of the study will be crucial in guiding the human hookworm vaccine clinical development plan, and we feel that to make an informed decision as to whether or not to proceed to pediatric trials, we must first assess the unblinded data in a timely fashion.

5.3.3 Reasons for Withdrawal and Discontinuation of Vaccinations

Subjects are free to withdraw from the study at any time and for any reason. Subjects who have received vaccine, regardless of the number of doses received, or who developed an AE or SAE will be encouraged to remain in the study to be followed for safety purposes.

Subjects may voluntarily withdraw their consent for study participation at any time and for any reason, without penalty.

A subject may withdraw or be withdrawn from the study for any of the following reasons:

- Medical disease or condition, or any new clinical findings for which continued participation, in the opinion of the Principal Investigator or appropriate co-investigator, would compromise the safety of the subject, or would interfere with the subject's successful completion of the study, or would interfere with the evaluation of responses.
- Subject no longer meets eligibility criteria.
- As deemed necessary by the Principal Investigator or appropriate co-investigator for noncompliance or other reasons.
- Subject withdrawal of consent.
- Subject lost to follow-up.
- Termination of the study.
- New information becomes available that makes further participation unsafe.

The second or third study vaccination may not be administered to a subject if any of the following criteria are met:

-
- Medical condition (including pregnancy) for which continued participation, in the opinion of the Principal Investigator or appropriate co-investigator, would pose a risk to the subject or would be likely to confound interpretation of the results.
 - Presence of signs or symptoms that could confound or confuse assessment of study vaccine reactogenicity. For subjects with injection site or systemic signs or symptoms, or with an acute illness, including an oral temperature greater than 38.0°C, the study vaccination should/may be postponed/deferred until signs, symptoms, or acute illness have resolved and if within the acceptable protocol-specified window for that visit. If outside this window, the Sponsor must first approve the second or third study vaccination and the documentation of approval should be filed in the subject's chart.
 - Any unresolved or continuing solicited or unsolicited Grade 3 adverse event. An unresolved or continuing Grade 1 or Grade 2 adverse event is permissible unless, in the opinion of the Principal Investigator or appropriate co-investigator, it would render study vaccination unsafe or interfere with the evaluation of responses.
 - Grade 3 clinical safety laboratory value that does not decrease to Grade 2 or less prior to the second or third study vaccination. Any clinical safety laboratory parameter may be re-evaluated only once at the central (clinical) laboratory prior to the second or third study vaccination. If the clinical safety laboratory value decreases to Grade 2 or less, the subject may receive the second or third study vaccination. The second or third study vaccination should be scheduled to occur within the acceptable protocol-specified window for that visit. If outside this window, the Sponsor must first approve the study vaccination and the documentation of approval should be filed in the subject's chart.
 - Severe or sustained reaction or disability related to the first study vaccination.
 - New onset of illness or condition that meets exclusion criteria.
 - Subject no longer meets eligibility criteria.
 - As deemed necessary by the Principal Investigator or appropriate co-investigator for noncompliance or other reasons.
 - Subject refusal of further study vaccination.
 - Subject withdrawal of consent.
 - Subject lost to follow-up.
 - Termination of the study.
 - New information becomes available that makes further participation unsafe.

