9.2 Methods and Timing for Assessing, Recording, and Analyzing Safety Parameters

9.2.1 Adverse Events

An adverse event (AE) includes any noxious, pathological or unintended change in anatomical, physiological or metabolic functions as indicated by physical signs, symptoms and/or laboratory-detected changes occurring in any phase of the clinical study, whether associated with the study vaccine or placebo, and whether or not considered vaccination related. This includes an exacerbation of pre-existing conditions and intercurrent illnesses.

All AEs will be graded for severity and relationship to study vaccine. A study clinician will be readily available for the duration of the trial to assess AEs. Should a subject call on a study clinician to report an AE, it will be fully documented in their study chart, and discussed with the Principal Investigator.

All AEs will be assessed by the investigator using the following protocol-defined grading system, as or described in Tables 2-5:

Grade 1:	Mild - No effect on activities of daily living; no medical intervention/therapy required
Grade 2:	Moderate - Partial limitation in activities of daily living (can complete $\geq 50\%$ of baseline); no or minimal medical intervention/therapy required
Grade 3:	Severe - Activities of daily living limited to $< 50\%$ of baseline; medical evaluation/therapy required

All AEs will have their possible relationship to study vaccine assessed using the following terms:

Definite:	Clear-cut temporal association, and no other possible cause.
Probable:	Clear-cut temporal association and a potential alternative etiology is not apparent.
Possible:	Less clear temporal association; other etiologies also possible.
Unlikely:	Temporal association between the AE and the vaccine or the nature of the event is such that the vaccine is not likely to have had any reasonable association with the observed illness/event (cause and effect relationship improbable but not impossible).
Not Related:	The AE is completely independent of vaccine administration; and/or evidence exists that the event is definitely related to another etiology.

The degree of certainty with which an AE can be attributed to administration of study vaccine will be determined by how well the event can be understood in terms of one or more of the following:

1. The event being temporally related with vaccination or reproduced on re-vaccination.

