9.2.2 Reactogenicity

Reactogenicity events are AEs that are known to occur with types of vaccine similar in composition to those being tested in this study. The following Toxicity Grading Scales will be used to grade solicited local (injection site) and systemic (subjective and quantitative) reactions:

Table 2: Assessment of Solicited or Expected Adverse Event Severity

Adverse Event	Grade	Severity
Pain at injection site	1	Easily tolerated, does not interfere with activity
	2	Repeated use of non-narcotic pain reliever for > 24 hours or interferes with daily activity
	3	Any use of narcotic pain reliever or prevents daily activity
Tenderness at injection site	1	Mild discomfort to touch
	2	Discomfort with movement
	3	Significant discomfort at rest
Erythema at injection site	1	25 mm – 50 mm
	2	51 mm – 100 mm
	3	> 100 mm
Induration/swelling at injection site	1	25 mm – 50 mm and does not interfere with daily activity
	2	51 mm – 100 mm or interferes with daily activity
	3	>100 mm or prevents daily activity
Fever (oral)	1	38.0°C – 38.4°C
	2	38.5°C – 38.9°C
	3	>39.0°C
Headache	1	Easily tolerated, does not interfere with daily activity
	2	Repeated use of non-narcotic pain reliever for >24 hours or interferes with daily activity
	3	Any use of narcotic pain reliever or prevents daily activity
Nausea	1	Easily tolerated, does not interfere with daily activity
	2	Interferes with daily activity
	3	Prevents daily activity
Vomiting	1	1-2 episodes in 24 hours and does not interfere with activity
	2	> 2 episodes in 24 hours or interferes with daily activity
	3	Prevents daily activity or requires outpatient IV hydration
Myalgia	1	Easily tolerated, does not interfere with daily activity
	2	Interferes with daily activity
	3	Prevents daily activity
Arthralgia	1	Easily tolerated, does not interfere with activity
	2	Interferes with daily activity
	3	Prevents daily activity
Urticaria	1	Requiring no medications
	2	Requiring PO or topical treatment, or IV medication or steroids for <24 hours
	3	Requiring IV medication or steroids for >24 hours
Mucocutaneous Reaction / Rash	1	Erythema; pruritus or localized macular rash
	2	Diffuse, maculopapular rash, dry desquamation
	3	Vesiculation or moist desquamation or ulceration

Table 3: Assessment of Unsolicited Systemic Adverse Event Severity

Systemic AE	Mild (Grade 1)	Moderate (Grade 2)	Severe (Grade 3)

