**With repeat testing at same visit

Table 5: Assessment of Laboratory Adverse Event Severity

HEMATOLOGY	Grade 1 (Mild)	Grade 2 (Moderate)	Grade 3 (Severe)
Hemoglobin Males Females	11.0 – 12.0 g/dL 10.3 – 11.3 g/dL	9.5 – 10.9 g/dL 8.5 – 10.2 g/dL	<9.5 g/dL <8.5 g/dL
Platelets	110,000 – 130,000/mm ³	90,000 – 109,999/mm ³	<90,000/mm ³
WBCs (increase)	10,800 – 15,000/mm ³	15,001 – 20,000/mm ³	<20,000/mm ³
WBCs (decrease)	2300 – 3200/mm ³	1400 – 2299/mm ³	<1400/mm ³
ANC (decrease)	750 – 1000/mm ³	500 – 749/mm ³	<500/mm ³
CLINICAL CHEMISTRIES	Grade 1	Grade 2	Grade 3
Serum creatinine Males Females	1.5 – 1.7 mg/dL 1.5 – 1.7 mg/dL	1.8 – 2.0 mg/dL 1.8 – 2.0 mg/dL	>2.0 mg/dL or requires dialysis >2.0 mg/dL or requires dialysis
ALT Males Females	58 – 115 U/L 64 – 128 U/L	116 – 230 U/L 129 – 255 U/L	>230 U/L >255 U/L

All local (injection-site) reactions occurring within the first 7 days after vaccination will be considered definitely related to vaccination.

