9.5 Halting Rules

If a dose of study vaccine is considered significantly reactogenic (see below and Section 9.2.2), dose escalation and/or additional vaccinations will be suspended until reviewed by the SMC, Independent Safety Monitor, DMID Medical Monitor, and IND sponsor (SVI). Any recommendation of the Independent Safety Monitor, DMID Medical Monitor, and SMC to resume or suspend further injections (either for an individual subject, an entire Group, or the full study) will be communicated in writing to the sponsor and Principal Investigator. All communications from the SMC will subsequently be forwarded by the investigators to the IRBs.

The following criteria will be used to define significant reactogenicity:

- One or more participants experience a protocol defined SAE that is determined to be possibly, probably, or definitely related to a study vaccine, **OR**,
- One or more participants experience a protocol defined AESI that is determined to be possibly, probably, or definitely related to a study vaccine, **OR**,
- One or more participants experience a protocol defined Grade 3 hypersensitivity reaction that is possibly, probably or definitely related to a study vaccine, **OR**,
- Two or more participants experience a protocol defined Grade 2 hypersensitivity reaction that is probably or definitely related to a study vaccine, **OR**,
- One or more participants in a single Group (i.e., Group 1, Group 2, etc.) experience the same objective physical finding or laboratory abnormality of Grade 3 or higher (with the exception of isolated Grade 3 erythema or swelling), that is determined to be probably or definitely related to a study vaccine, **OR**,
- Two or more participants in a single Group experience the same Grade 2 or higher safety laboratory abnormality or Grade 3 clinical AE that is possibly, probably or definitely related to a study vaccine.

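### Section 5.3.3 governs doses 2 and 3, but its severe-reaction bar names only the first vaccination, so one subject's resolved severe reaction to dose 2 is no explicit bar to dose 3

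*Protocol*

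**What the plan says.** The list in Section 5.3.3 opens with a scope that covers both later doses: "The second or third study vaccination may not be administered to a subject if any of the following criteria are met". The criterion on reactions within that list is narrower: "Severe or sustained reaction or disability related to the first study vaccination". Nothing in the section explains why a reaction to dose 2 should be treated differently.

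Three other parts of the protocol bear on the point.

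- **Grading.** Section 9.2.1 ties the word severe to Grade 3 ("Severe - Activities of daily living limited to" less than 50% of baseline). Solicited reactions have their own scale, "Table 2: Assessment of Solicited or Expected Adverse Event Severity".
- **Causality.** Section 9.2.2 settles relatedness for early local reactions: "All local (injection-site) reactions occurring within the first 7 days after vaccination will be considered definitely related to vaccination".
- **Halting rules.** Section 9.5 suspends dosing pending review when one participant has the "same objective physical finding or laboratory abnormality of Grade 3 or higher", if at least probably related and "with the exception of isolated Grade 3 erythema or swelling". Suspension also follows when "Two or more participants in a single Group experience the same Grade 2 or higher safety laboratory abnormality or Grade 3 clinical AE", if at least possibly related. A single related SAE, related adverse event of special interest or related Grade 3 hypersensitivity reaction is enough as well.

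**The concern.** A list that decides on dose 3 should take account of what happened after dose 2, and this one names dose 1 only. The purpose of the criterion is that a severe related reaction should not rest on case-by-case judgement. As written, that protection lapses once the second dose has been given, although a reaction to the second exposure is no less informative about the third.

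Safety and reactogenicity are the primary objective. Section 2.2.2 says that Na-APR-1 (M74) had not yet been given to people living in a hookworm-endemic area. All 60 subjects are due a third dose under this list. What is at stake is re-exposure of an individual subject to the same product after a severe reaction. No endpoint, analysis or sample-size figure depends on it.

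**Working it through.** The plan gives no figure to reproduce here. The check is the interval between doses 2 and 3, followed by a reading of each other safeguard against a concrete case.

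**Interval between doses 2 and 3** (windows from Section 7.3 and Appendix A)

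- Dose 2: Day 56 ± 7, so Day 49 to Day 63.
- Dose 3: Day 112 ± 14, so Day 98 to Day 126.
- Shortest: 98 − 63 = 35 days. Nominal: 112 − 56 = 56 days. Longest: 126 − 49 = 77 days.
- Dosing outside the window needs sponsor approval (Sections 5.3.3 and 6.3), so an interval can differ from these limits only by exception.

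**Test case.** One subject has severe injection-site pain within 7 days of dose 2. It is not an SAE, is not allergic, and resolves well before dose 3. Under Section 9.2.2 it is definitely related.

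| Safeguard | Does it bar dose 3 in this case? |
|---|---|
| Reaction criterion, 5.3.3 | No; it names the first vaccination only |
| Grade 3 adverse event criterion, 5.3.3 | No; the event must still be present at dose 3, at least 35 days later |
| Signs or symptoms criterion, 5.3.3 | No; nothing is present at dose 3, and otherwise the remedy is deferral |
| Medical condition and as-necessary criteria, 5.3.3 | Only if the investigator so judges |
| Exclusion 16, if re-applied after entry | No; it covers severe allergic reactions only |
| Halting rule for one subject's objective finding, 9.5 | No; pain is a reported symptom |
| Halting rule for Grade 3 clinical events, 9.5 | No; it needs two participants in the same Group |
| Monitors' recommendation for an individual, 5.3.5 and 9.5 | Possible, but discretionary |

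Severe headache gives the same result, except that its relatedness has to be assessed. Isolated Grade 3 erythema or swelling also gives the same result, because the one-subject rule in Section 9.5 exempts it.

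**Sustained Grade 1 or 2 reaction to dose 2.** If it is still present at dose 3, Section 5.3.3 allows dosing unless the investigator objects, or defers the dose until it clears. If it has cleared, no criterion refers to it. A sustained reaction to dose 1 is named as a bar.

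**What is caught after dose 2.** The following do not fall through the gap:

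- a persistent or significant disability, which is an SAE under Section 9.2.3 and triggers suspension under 9.5 if related;
- any other related SAE, or a related Grade 3 hypersensitivity reaction;
- an objective Grade 3 finding that is at least probably related and is not isolated erythema or swelling;
- a Grade 3 event still continuing at dose 3.

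The Section 9.5 rules suspend dosing for review. They are not themselves permanent bars for the individual.

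**The case against.** The best defence is that little is left uncovered. Disability, serious events, hypersensitivity and most objective Grade 3 findings are dealt with under Section 9.5. Ongoing severe events are dealt with in Section 5.3.3 itself. The investigator may withhold a dose for any subject, and the monitors may recommend suspension for one individual. This stands, and it is why the gap is narrow. It does not close the gap, because what remains after dose 2 is discretion where the plan chose an explicit rule after dose 1.

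A second objection concerns the word severe. A reader might infer from the Section 9.2.1 label that every Grade 3 local reaction within 7 days of dose 1 is an automatic bar, and might then count how many Table 2 reactions escape after dose 2. The documents do not support that step. The reaction criterion cites no grade. A neighbouring criterion bars Grade 3 events only while they last, and it would be largely redundant for related reactions to dose 1 if any resolved Grade 3 reaction were already a bar. A count would also need debatable choices, such as whether tenderness on examination is objective and whether induration shares an exemption that names only erythema and swelling. No count is therefore given. The asymmetry survives, because whatever severe means, the criterion applies it to the first vaccination only.

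A reader might also infer that the two criteria on meeting exclusion or eligibility criteria conflict with the laboratory criterion, which permits dosing at Grade 2 or below. That is not supported as a fault. Section 5 ties the eligibility criteria to enrollment, Section 7.2 has them verified at Day 0, exclusions 2 and 21 say so where they run through dosing, and the laboratory criterion is the specific rule for doses 2 and 3.

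**Conclusion.** The point holds in a narrow form and is minor. No mandatory rule bars dose 3 after one subject's severe, non-serious, non-allergic reaction to dose 2 that has resolved by the time of dose 3, nor after a sustained Grade 1 or 2 reaction to dose 2. Both are left to investigator or monitor discretion.

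The wording and the 35-to-77-day interval are certain. How often the gap would matter is not. The protocol gives no Grade 3 rate, and it describes the related events in the earlier trials as mostly mild-to-moderate injection-site pain and tenderness (Sections 2.1.6 and 2.1.9). Few subjects are likely to be affected. If severe is meant as something graver than Grade 3, the gap shrinks further, because graver events are more likely to meet a Section 9.5 rule.

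It would be wrong to infer that subjects are unprotected after dose 2. The safeguards listed above remain in force.

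**What to change.** In the Section 5.3.3 reaction criterion, replace the reference to the first vaccination with 'any prior study vaccination' and leave the rest of the sentence as it is. No other criterion needs to change, and the fix works whichever reading of severe the sponsor intends.

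The change needs a protocol amendment submitted to the IRBs (Section 15.6). It adds no procedures and no subjects. Its price is that dose 3 may occasionally be withheld from a subject who would otherwise have received it at the investigator's discretion. Each such subject is 1 of 5 in an arm for the three-dose antibody response at Day 126. Under Section 6.3 that subject is still asked to return for safety visits and blood samples. The plan already accepts the same kind of loss for reactions to dose 1.
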